### 6.2. Rescreening

Patients may only be rescreened with the approval of the Sponsor. If a patient is rescreened, all screening assessments must be repeated except tumor tissue sample (as applicable). Imaging assessments, echocardiogram/MUGA, and dermatologic examinations do not need to be repeated if performed within 21 days of the first dose of study drug. Patients may only be rescreened once. If a patient is rescreened, the screening window will begin once the first rescreening assessment has been initiated.

### 6.3. Treatment Period

Patients will be randomized in the study after confirmation of all eligibility criteria. The first dose of study drug must be administered in the clinic on Cycle 1 Day 1. Study visits during the Treatment Period will occur as shown in [Table 1](#) (schedule of assessments). Patients will be outpatients during the Treatment Period. All visits must occur within the windows specified.

Patients who prematurely discontinue study drug must return for an EOT Visit within 7 days after the last dose of study drug.

### 6.4. Follow Up

Patients will be contacted by phone call for the Safety Follow-up Visit 30 days (+5 days) after the last dose of study drug to assess AEs; medications, including anticancer treatments; and procedures (see Section [6.11.11](#) for further details). Patients will be contacted by phone call for OS and PFS2 (see Section [6.10.2](#) for further details).

### 6.5. Lost to Follow Up

A patient will be considered lost to follow up if both of the following occur:

- Patient misses 2 consecutive study visits and is subsequently unable to be contacted by phone call (3 documented attempts by phone within 2 weeks following the second missed visit).
- Patient does not respond within 2 weeks to a registered letter sent after the 3 attempted phone contacts.

### 6.6. Study Assessments

The study specific assessments are detailed in this section and the schedule of assessments are outlined in [Table 1](#).

Additional unscheduled safety or efficacy assessments may be performed at any time as clinically indicated to determine the relevance of specific findings and/or the duration of events.

### 6.6.1. Timing of Assessment

The EORTC QLQ-C30, EuroQol 5 Dimension 5 Level (EQ-5D-5L), DLQI, GP5 question from FACT-G, and the memory and concentration parts of the PRO-CTCAE questionnaires must be performed before the patient is evaluated by the Investigator or designee on the day of the scheduled visit. If the dermatologic examination or imaging assessments are completed within 7 days of the scheduled visit and the patient is not evaluated by the Investigator or designee, the questionnaires do not need to be completed on that day. The GP5 question from FACT-G will be completed first followed by EORTC-QLQ-C30, DLQI, EQ-5D-5L and the memory and concentration parts of the PRO-CTCAE.

All other assessments may be completed in any order as shown in [Table 1](#) (schedule of assessments).

### 6.7. Informed Consent Procedure

Each patient must sign and date a study-specific ICF before any study specific procedures can be performed. The ICF will comply with all applicable regulations governing the protection of patients. An ICF, approved by the Sponsor and the site's Institutional Review Board (IRB)/Independent Ethics Committee (IEC)/Research Ethics Board (REB) must be used. The Investigator or designee must document the consenting process, including the date when the ICF was signed in the patient's source document.

### 6.8. Assigning Patient Number

A unique patient identification number (patient number) will be assigned to each patient once informed consent is obtained. Detailed instructions on assigning patient numbers will be provided in the Study Reference Manual. If a patient is rescreened, the patient retains the original patient number.

### 6.9. Demographics and Medical History

Demographic information must be collected at screening.

Cancer history and prior treatment (including reason for discontinuation) must be obtained during screening. Cancer history will include:

- Known histologic diagnosis of GIST
- Tumor mutational status
- All prior cancer treatment regimens, including:
  - Surgery (including tumor tissue sample[s]): include date(s), site(s), and extent of resection (e.g. tumor tissue sample only, R0, R1, or R2)
  - Prior imatinib therapy: include dates of treatment, including dose and dosing regimen, reason for treatment (e.g. adjuvant therapy or for metastatic disease), best response, date of disease progression or date and reason for treatment discontinuation other than disease progression.
  - Radiation therapy: include the site(s) treated, total dose(s), date(s) of treatment, and response(s)

- Other procedures, such as radiofrequency ablation (if applicable)

Molecular pathology report with mutational status of KIT/PDGFRA must be provided to the Sponsor for review prior to randomization. If molecular pathology report is not available or insufficient, an archival tumor tissue sample or fresh biopsy is required for mutation status confirmation prior to randomization. Specific instructions will be provided in the Study Reference Manual.

Medical history, including any significant conditions or diseases that stopped at or prior to informed consent, must be elicited from each patient during screening. Based on the medical history, the patient must be assessed for any disqualifying medical conditions as specified in the inclusion and exclusion criteria. The medical history shall include a complete review of systems, past medical and surgical histories, and any allergies. Ongoing conditions are considered concurrent medical conditions; if possible, the start date for these comorbidities must be documented.

## **6.10. Efficacy**

### **6.10.1. Radiologic Imaging**

All patients will have radiographic tumor evaluation by CT scans of the pelvis, abdomen, and chest according to [Table 1](#) (schedule of assessments). Radiologic imaging performed as standard of care prior to informed consent may be used as the screening assessment as long as the imaging was performed within 21 days prior to the first dose of study drug. Radiologic imaging may be performed up to 7 days prior to the corresponding study visit or post dose at the study visit. Following Cycle 7 Day 1, an initial indication of a PR or CR based on investigator assessment must be confirmed  $\geq 4$  weeks following initial response. Magnetic resonance imaging (MRI) scans of the abdomen/pelvis and CT scan without contrast of the chest may be used for patients who are allergic to radiographic contrast media or per Investigator's discretion based on the best interest of the patient after discussion with the Sponsor. Additionally, for patients whose local regulatory authority and/or ethics committee has not approved use of CT scans, MRIs may be used. Throughout the study, the same assessment technique used on a patient at screening must continue to be used for that patient for the duration of their study participation unless there is a safety risk as determined by the Investigator. Ultrasound scanning is not an acceptable substitute for CT scanning.

Copies of all imaging scans must be obtained and sent to an independent imaging vendor designated by the Sponsor as outlined in a separate protocol specific manual. The independent imaging vendor will assess the quality of the images and be responsible for performing an independent radiologic review.

The independent imaging vendor must ensure that the independent radiologic reviewer remains blinded to the local assessment from the Investigator. This and all other imaging procedures will be documented in a protocol specific review charter agreed upon between the Sponsor and the independent imaging vendor before initiation of any independent radiologic reviews.

The independent radiologic reviewer and Investigator will assess tumor response using mRECIST (see Section 9.2.1.1). Response as determined by the Investigator will be recorded in the eCRF. Data from the independent radiologic review (IRR) will be used for the primary endpoint analysis. The IRR will also assess tumor response using Choi criteria, and this will be used for a secondary endpoint. More details on image acquisition guidelines and radiographic assessment will be provided in a separate protocol specific manual.

**Confirmation of Disease Progression (by IRR):** [REDACTED]

[REDACTED] A scan is not required at the EOT visit if disease progression was previously confirmed by independent radiologic review.

**Confirmation of No Disease Progression (by IRR):** If the independent radiologic reviewer confirms that there is no disease progression, the patient will continue to receive study drug.

- If the Investigator determines clinical progression based upon clinical deterioration and wishes to end treatment, a scan must be performed prior to treatment discontinuation. The scan must be submitted to for independent radiologic review. The basis for determination of progression due to clinical deterioration must be documented in the patient's source documents and eCRF. If the Investigator's assessment determines disease progression per mRECIST, the Investigator should wait for confirmation from the independent radiologic review before discontinuing the patient from treatment.
- If the Investigator wishes to end treatment due to local progression based on mRECIST, without confirmation of progression by independent radiographic review, or before the independent read results are available, the Investigator must reach out to the Sponsor Medical Monitor to discuss.

**6.10.2. Overall and PFS2 Survival Follow-Up by Phone Call**

All patients will be followed until withdrawal of consent or death from any cause. After the Safety Follow-Up Visit, patients will be contacted every 3 months ( $\pm 1$  month) to collect long-term survival data, including OS and PFS2 (i.e. next line of therapy, start date of next line therapy, and the date of progression on the next line of therapy).

**6.10.3. Patient Reported Outcome Measurements****6.10.3.1. European Organisation for Research and Treatment of Cancer Quality of Life Questionnaire for Cancer 30-item (EORTC QLQ-C30)**

The EORTC QLQ-C30 is a validated, standardized, patient-completed questionnaire used extensively in international clinical studies and developed to assess health-related QOL in patients with cancer (25). The time required for completion is approximately 12 minutes. Validated translations will be provided for sites in non-English speaking countries.

The questionnaire is composed of multi-item and single-item scales. These include 5 functional scales (physical functioning, role functioning, emotional functioning, social functioning, cognitive functioning), 9 symptom scales (fatigue, nausea and vomiting, pain, dyspnea, insomnia, appetite loss, constipation, diarrhea, and financial difficulties), and a global health status/QOL scale.

The patient is asked to rate his or her experience for a particular item during the last week by selecting Likert scale response options of "not at all," "a little," "quite a bit," or "very much." Two items assess the patient's global health status over the past week using self-reported scales with 1 representing "very poor" and 7 representing "excellent".

Patients will be asked to complete EORTC QLQ-C30 in their native language using an electronic patient reported outcome (ePRO) system before dosing at the visits indicated in [Table 1](#) (schedule of assessments). If the EORTC-QLQ-C30 is not available in the patient's native

language, the patient will be exempt from taking the questionnaire. Patient-entered data will not be modified by the Investigator or site staff, ePRO vendor, CRO or Sponsor.

### **6.10.3.2. Dermatology Life Quality Index**

The Dermatology Life Quality Index (DLQI) is a validated questionnaire used to measure the impact of skin symptoms on the QOL of an affected person (32). There are 10 questions, covering the following topics: symptoms, embarrassment, shopping and home care, clothes, social and leisure, sport, work or study, close relationships, sex, and wider treatment consequences. Each question refers to the impact of the skin disease on the patient's life over the previous week. Each question is scored at four levels from "Not at all" (0), through "A little", and "A lot", to "very much" (3), giving a possible summary score range from 0 (meaning no impact of skin disease on QOL) to 30 (meaning maximum impact on QOL). A difference of four is considered to be clinically significant in inflammatory skin disease. Validated translations will be provided for sites in non-English speaking countries.

Patients will be asked to complete DLQI in their native language using an ePRO system before dosing at the visits indicated in Table 1 (schedule of assessments). If the DLQI is not available in the patient's native language, the patient will be exempt from taking the questionnaire. Patient-entered data will not be modified by the Investigator or site staff, ePRO vendor, CRO or Sponsor.

### **6.10.3.3. GP5 Question from FACT-G**

The GP5 burden-of-side-effects question, a part of the Functional Assessment of Chronic Illness Therapy (FACIT) Functional Assessment of Cancer Therapy - General (FACT-G) questionnaire, is a validated, standardized, patient completed question used extensively in international clinical studies (33). It was developed to assess health related QOL in patients with cancer. The time required for completion is approximately 20 seconds. The question is completed by the patient's selection of one of the following options of "not at all," "a little bit," "somewhat," "quite a bit," and "very much". Validated translations will be provided for sites in non-English speaking countries.

Patients will be asked to complete the GP5 question from FACT-G in their native language using an ePRO system before dosing at the visits indicated in Table 1 (schedule of assessments). If the GP5 question from FACT-G is not available in the patient's native language, the patient will be exempt from taking the questionnaire. Patient-entered data will not be modified by the Investigator or site staff, ePRO vendor, CRO or Sponsor.

### **6.10.3.4. Memory and Concentration Portions of PRO-CTCAE Library**

The NCI-PRO-CTCAE measurement system was developed to gather symptomatic AEs by patient self-reporting (34). The NCI-PRO-CTCAE library is comprised of 124 items representing 78 symptomatic AEs. The NCI-PRO-CTCAE items evaluate symptom attributes such as symptom occurrence, frequency, severity, and interference with daily activities, and are intended to be complementary to the items in the NCI's CTCAE. Validated translations will be provided as available for specific non-English speaking countries. If validated translations are not available for the patient, the patient will be exempt from completing this questionnaire.

Patients will be asked to complete questions 46 and 47 of the PRO-CTCAE in their native language, if available, using an ePRO system before dosing at the visits indicated in Table 1 (schedule of assessments). The time to fill out all the questions is less than a minute. Patient-

entered data will not be modified by the Investigator or site staff, ePRO vendor, CRO or Sponsor.

Patients are asked to rate the severity of problems with concentration/memory on a five level Likert scale going from None to Very severe. They are also asked to rate how much those problems interfered with their usual activities on a five-level Likert Scale going from Not at all to Very much.

#### **6.10.3.5. EuroQol 5-Dimension 5-Level (EQ-5D-5L)**

The EQ-5D-5L is a validated, standardized, patient-completed questionnaire developed by the EuroQol group and used commonly in clinical studies to provide a measure of patient utility for clinical and economic appraisals (26). The time required for completion is approximately 2 minutes. Validated translations of the EQ-5D-5L will be provided for sites in non-English-speaking countries.

The first 5 items of the EQ-5D-5L measure the health dimensions of mobility, ability to conduct self-care, ability to conduct usual activities, pain/discomfort, and anxiety/depression. The patient will select from 5 response levels (no problems, slight problems, moderate problems, severe problems, extreme problems) to rate their level of difficulty on that dimension that day.

The sixth item is a EuroQol visual analogue scale (EQ-VAS). The EQ-VAS records the patient's self-rated health on a vertical scale with endpoints labeled "the best health you can imagine" and "the worst health you can imagine." This information can be used as a quantitative measure of health as judged by the individual patient. A patient is asked to "mark an X on the scale to indicate how your health is TODAY" and "write the number you marked on the scale in the box below."

Patients will be asked to complete EQ-5D-5L in their native language using an ePRO system before dosing at the visits indicated in Table 1 (schedule of assessments). If the EQ-5D-5L is not available in the patient's native language, the patient will be exempt from taking the questionnaire. Patient-entered data will not be modified by the Investigator or site staff, ePRO vendor, CRO or Sponsor.

### **6.11. Safety**

The safety profile will be assessed based on physical examinations, ECOG PS, changes from baseline in vital signs, ECGs, LVEF based on echocardiogram/multigated acquisition scan (MUGA), dermatologic examination, and clinical laboratory tests, and the reporting of AEs.

#### **6.11.1. Physical Examinations**

A full physical examination will be performed at screening. A full physical examination includes a review of the following systems: head/neck/thyroid, eyes/ears/nose/throat, respiratory, cardiovascular, lymph nodes, abdomen, skin, musculoskeletal, and neurological. Breast, anorectal, and genital examinations will be performed when medically indicated. At all other visits, examinations will be driven by clinical findings and/or patient complaints. After screening, any clinically significant abnormal findings in physical examinations must be reported as AEs.

### 6.11.2. Eastern Cooperative Oncology Group Performance Status

ECOG PS (27) will be assessed according to the schedule of assessments in Table 1 (schedule of assessments). ECOG PS may be performed pre or post dose.

### 6.11.3. Vital Signs, and Weight and Height

Vital sign measurements, height, and weight will be performed according to Table 1 (schedule of assessments). Vital sign measurements will include sitting blood pressure, pulse, respiratory rate, and body temperature. These will be assessed following a 5-minute rest (seated or supine position).

### 6.11.4. Electrocardiograms

Digital, 12-lead ECGs will be performed with central over-reading according to the schedule of assessments in Table 1 (schedule of assessments). All sites will be provided with an ECG machine and associated materials by the central ECG diagnostic service.

Performance of all ECGs must adhere to the following guidelines:

- All standard digital ECGs must be performed after the patient has been in the supine or semi-recumbent position for at least 15 minutes. The 15-minute rest period will start after the placement of the ECG leads.
- The ECG must be performed before the dose of study drug.

A hard copy of the ECG must be printed and signed by the Investigator at the site.

ECG data will be transmitted to the central ECG diagnostic service and all interval measurements will be reviewed and adjusted using the central ECG core labs methodology by a trained ECG analyst. A cardiologist at the central ECG diagnostic service will then review each ECG to confirm if intervals were calculated correctly and to provide an interpretation. A report containing this information will be provided to the site for review and signature by the Investigator. This report will be filed with the machine ECG report for each visit in the patient's source documents. The values reported by the central ECG diagnostic service will be used for data analysis.

Heart rate and the following ECG intervals will be captured in the database:

- PR interval
- QT, QT interval corrected using Bazett's formula (QTcB) ( $QTcB = QT/RR^{0.50}$ ) and QT interval corrected by Fridericia's formula (QTcF) ( $QTcF = QT/RR^{1/3}$ ) intervals
- QRS duration
- RR interval

The central ECG diagnostic service's standard reference ranges will be used throughout the study.

### 6.11.5. Echocardiograms/Multigated Acquisition Scans

Echocardiograms or multigated acquisition scans (MUGAs) will be performed according to [Table 1](#) (schedule of assessments). Echocardiogram or MUGA performed as standard of care prior to informed consent may be used as the screening assessment as long as the echocardiogram or MUGA was performed within 28 days prior to the first dose of study drug. The same modality (echocardiogram or MUGA) must be used throughout the study. LVEF must be documented in the patient's source documents and eCRF.

### 6.11.6. Dermatologic Examination

All patients will be assessed by a consulting dermatologist for skin lesions, especially for SCC, actinic keratosis, and keratoacanthomas, according to [Table 1](#) (schedule of assessments) and as clinically indicated. The examinations must include the entire skin. Any dermatologic exam that meets the protocol criteria that was performed as standard of care prior to informed consent may be used as the screening assessment as long as the exam was performed within 21 days prior to the first dose of study drug. Any new or changing skin lesions noted during the course of treatment must be documented in the patient's source documents and eCRF. In case of suspected SCC or keratoacanthomas, a skin biopsy must be taken for confirmation of diagnosis by a certified pathologist at the clinical site. Samples with confirmed SCC or keratoacanthoma lesions will be sent to a central laboratory for histopathological and/or molecular analysis. Comparative analysis of all patient lesions will be performed to investigate signifying aberrant oncogene pathway(s) and their potential relationship to the study drug. For more information on the management of SCC, actinic keratosis, and keratoacanthomas, considered to be AESIs, see [Section 7.9](#).

### 6.11.7. Clinical Laboratory Tests

Blood and urine samples will be collected according to [Table 1](#) (schedule of assessments) and analyzed at a central laboratory. All blood samples must be collected while patients are in a seated or supine position. Specific instructions for the collection, processing and shipment of samples will be provided in a separate laboratory manual. Laboratory test results that are abnormal and considered clinically significant must be reported as AEs ([Section 7.7.1](#)). Screening laboratory results from the central laboratory must be available before randomization. All samples must be collected in accordance with acceptable laboratory procedures and graded for toxicity as defined by the National Cancer Institute Common Terminology Criteria for Adverse Events (NCI-CTCAE), Version 5.0.

Available local laboratory test results will be used for treatment management decisions (dose interruptions or dose modifications [[Section 5.4.2](#)]) and initial assignment of CTCAE grading. Central laboratory results will be used for final assignment of CTCAE grading. In the case of different grades associated with local versus central laboratory results for AEs, the Investigator should determine which laboratory values will be used for documenting grading of AEs. The local versus central laboratory result with the highest grade should be considered to document grading of AEs.

The safety laboratory tests are provided in [Table 11](#).

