**Table 10: DCC-2618 Dose Modifications for Treatment Related Adverse Events Not Mentioned Above**

Toxicity Grade	Management Guideline
Any Grade 3 or 4	Interrupt DCC-2618 dosing until event has resolved to Grade 1 or baseline Once the AE returns to Grade 1 or baseline, reduce DCC-2618 by 1 dose level If a patient tolerates the reduced dose without recurrence of the event for at least 28 days, consider re-escalating the dose of DCC-2618 to the prior dose level
Asymptomatic/Not clinically significant Grade 3 or 4 laboratory AEs (including CPK and lipase) that persist ≤10 days	Closely monitor for clinical symptoms and continue DCC-2618 at the current dose level. Repeat labs within 10 days.
Asymptomatic/Not clinically significant Grade 3 or 4 laboratory AEs (including CPK and lipase) that persist >10 days	Closely monitor for clinical symptoms; for Grade 4 events, interrupt DCC-2618 until the event returns to Grade 3 Asymptomatic Grade 3 or Grade 4 elevations of plasma enzyme: lipase or CPK do not require dose interruption Once the AE returns to Grade 3, resume DCC-2618 at the current dose level or consider reducing by 1 dose level per Investigator discretion after discussion with the Sponsor.
Clinically Significant Grade 3 or 4 laboratory AEs (including CPK and lipase)	Interrupt the DCC-2618. If the Investigator assesses that restarting DCC-2618 is in the patient's best interest, the Sponsor must be contacted for discussion and determination if restarting is allowed.

AE=adverse event; CPK=creatinine phosphokinase

 The rules for dose modifications for laboratory AEs will be based on local laboratory results.

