### **5.11. Blinding and Unblinding**

This is an open-label study.

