## 7.7. Additional Points to Consider for Adverse Events

### 7.7.1. Clinically Significant Assessments

Study assessments including laboratory tests, ECGs, physical examinations, and vital signs must be assessed and those deemed as clinically significant must be documented as an AE. When possible, a clinical diagnosis for the study assessment must be provided rather than the abnormal test result alone (e.g. urinary tract infection, anemia). In the absence of a diagnosis, the abnormal study assessment itself may be listed as the AE (e.g. bacteria in urine or decreased hemoglobin).

An abnormal study assessment is considered clinically significant if the patient has 1 or more of the following:

- Worsening, from baseline, concomitant signs or symptoms related to the abnormal study assessment
- Further diagnostic testing or medical/surgical intervention is required
- A change in the dose of study drug, if study drug is withheld, or discontinuation from study drug occurs

Repeat testing to determine whether the result is abnormal, in the absence of any of the above criteria, does not necessarily meet clinically significant criteria. The determination of whether the study assessment results are clinically significant must be made by the Investigator.

**A laboratory abnormality judged to be Grade 4, in itself, may not constitute an SAE unless the clinical status of the patient indicates a life-threatening AE.**

Symptoms of the disease under study must not be recorded as AEs as long as they are within the normal day-to-day fluctuation or expected progression of the disease, including significant worsening unless the deterioration was unexpected, and are part of the efficacy data to be collected in the study.

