9.5. Clinical Laboratory Data

Clinical laboratory measurements will be collected from screening until the end of treatment visit (within 7 days of the last dose). Laboratory values will be graded for severity according to the National Cancer Institute Common Terminology Criteria for Adverse Events (NCI-CTCAE), Version 5.0.

Table 3: Safety Laboratory Tests

Serum Chemistry	Hematology	Urinalysis
Blood urea nitrogen	Hemoglobin	Urine protein
Creatinine	 Mean corpuscular hemoglobin 	Urine blood
Sodium	 Mean corpuscular hemoglobin 	Specific gravity
Potassium	concentration	Urine ketones
Calcium	Mean corpuscular volume	Urine glucose

CONFIDENTIAL Page 26 of 29

Magnesium	Hematocrit
Phosphorus	Platelets
Total and direct bilirubin	Leukocytes
Alkaline phosphatase	Reticulocytes
Aspartate aminotransferase	Differential (absolute):
Alanine aminotransferase	Eosinophils
Lactate dehydrogenase	Basophils
Total protein	Neutrophils
Albumin	• Lymphocytes
Creatine Phosphokinase	Monocytes
Globulin	
Triglycerides	Coagulation Studies (for patients
Lipase	taking anticoagulants)
Amylase	Activated partial thromboplastin
TSH	time
T3	Prothrombin time
T4	International Normalized Ratio

Assessments will be summarized by time point utilizing continuous descriptive statistics as appropriate. In addition, the numeric changes from baseline will be summarized for continuous parameters. For categorical parameters, the number and percentage of patients with assessment will be displayed.

Changes in severity from baseline will be summarized by the maximum shift in CTCAE severity grade from baseline to post baseline.

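### When local and central laboratory grades differ, Protocol 6.11.7 gives conflicting rules for the adverse event grade and the SAP names no source, so grade-specific laboratory AE tables could differ by arm for reasons other than the drug.

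*Protocol*

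**What the plan says.** Protocol 6.11.7 has the scheduled blood and urine samples analysed centrally and graded by CTCAE Version 5.0. Available local results serve treatment decisions and give the initial grade. Three statements then follow in order:

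- "Central laboratory results will be used for final assignment of CTCAE grading".
- Where local and central grades for an AE differ, "the Investigator should determine which laboratory values will be used for documenting grading of AEs".
- The paragraph then closes with a further instruction on such pairs: "The local versus central laboratory result with the highest grade should be considered to document grading of AEs".

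Protocol 5.11 states: "This is an open-label study". Whether an abnormal result counts as an AE at all is settled elsewhere, in Protocol 7.7.1: "The determination of whether the study assessment results are clinically significant must be made by the Investigator".

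SAP 9.2 tabulates AEs by maximum severity grade, including a 1/2, 3/4 and 5 grouping, without saying which laboratory's result fixes the grade. SAP 9.5 says "Laboratory values will be graded for severity according to the National Cancer Institute" criteria and plans a table of the maximum grade shift from baseline, again without naming the source. SAP 10.2.2 pools local data for vital signs, dermatologic examination, ECG and echocardiogram/MUGA, but does not mention blood or urine tests.

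**The concern.** Comparing the two safety profiles is a stated secondary objective, and tables by grade are a main output for it. If the protocol gives more than one grade for the same pair of results, two sites can record the same patient differently and both be compliant. With open-label treatment, the person making the choice knows the arm.

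The documents also show a way in which local testing could differ by arm. For DCC-2618, the footnote to Protocol Table 10 says "The rules for dose modifications for laboratory AEs will be based on local laboratory results", and for certain asymptomatic Grade 3 or 4 laboratory AEs the table adds "Repeat labs within 10 days". For sunitinib, Protocol 5.4 refers to the package insert or institutional guidelines. Under a highest-of-two rule, the arm with more local results has more chances to record a higher grade. A Grade 3/4 difference could then partly reflect how often patients were tested locally, or how sites resolved disagreements.

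**Working it through.** The plan has no figure to reproduce here. The check is a comparison of the rules, followed by an illustration.

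**Step 1. Apply each rule to every discordant pair.** With Grades 1 to 4 from each laboratory there are 4 × 4 = 16 pairs, of which 4 agree and 12 disagree.

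| Pair type | Pairs | Central-final | Highest-grade | Investigator choice |
|---|---|---|---|---|
| Local above central | 6 | central (lower) | local (higher) | either |
| Central above local | 6 | central (higher) | central (higher) | either |

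Central-final and highest-grade conflict in the 6 pairs where local exceeds central and agree in the other 6. Investigator choice fixes none of the 12.

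**Step 2. What can move.** These sentences decide the grade. AE status rests on clinical significance (Protocol 7.7.1). A change from one of Grades 1 to 4 to another therefore alters tables by grade and leaves the count of patients with the AE unchanged.

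**Step 3. Illustration on the document's own counts.** Protocol Table 3 (Phase 1, GIST patients at 150 mg QD, N = 114) lists lipase elevation in 7, 3, 9 and 2 patients at Grades 1 to 4. That is 21/114 = 18.4% at any grade and (9 + 2)/114 = 9.6% at Grade 3-4. Take these as the reference grades. The share q that shifts by one grade is an assumption, because the documents give no discordance rate.

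- Upward (highest-grade rule; a share q of Grade 2 becomes Grade 3): (11 + 3q)/114.
- Downward (the investigator takes a lower local grade; a share q of Grade 3 becomes Grade 2): (9(1 − q) + 2)/114.

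| q | Upward, Grade 3-4 | Downward, Grade 3-4 | Gap | Any grade |
|---|---|---|---|---|
| 10% | 11.3/114 = 9.9% | 10.1/114 = 8.9% | 1.2/114 = 1.1 points | 18.4% |
| 20% | 11.6/114 = 10.2% | 9.2/114 = 8.1% | 2.4/114 = 2.1 points | 18.4% |
| 50% | 12.5/114 = 11.0% | 6.5/114 = 5.7% | 6.0/114 = 5.3 points | 18.4% |

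The gap column is the extreme case for this illustration: identical underlying results in both arms, with every disagreement resolved upward in one arm and downward in the other. It bounds what the wording permits under these assumptions and is not a forecast.

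**Step 4. Does the SAP settle it?** No. SAP 9.2 and 9.5 cite the CTCAE version but no laboratory source, and the local-data rule in SAP 10.2.2 does not reach blood or urine tests.

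**The case against.** The strongest reply is that the paragraph can be read as coherent. The second and third sentences both concern AE grading, so they can be taken as one rule: the investigator decides, guided toward the higher grade. The central-final sentence mentions only CTCAE grading, and the preceding paragraph applies that grading to samples, so it may concern laboratory values rather than AE forms. Protocol 7.2 in any case makes the investigator responsible for the severity of every AE.

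Much of this stands. A reader might infer three mutually incompatible rules, but the documents support only one clear conflict, central-final against highest-grade when local is higher, together with a discretionary sentence. The split between laboratory values and AE forms is plausible, but the text does not state it. Even on that reading, AE grading remains discretionary.

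Other stronger inferences also fail:

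- That overall laboratory AE rates are affected: they are not, by Step 2.
- That the shift tables depend on the investigator's knowledge of the arm: SAP 9.5 grades laboratory values, and scheduled samples go to the central laboratory, so central is the natural source. What is missing is the statement.
- That local tests are drawn because clinicians are worried, or more often in one arm: neither document says when or why they are drawn. Table 10 shows only that practice could differ.
- That discretion can only push rates up: the investigator could also choose a lower local grade.

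**Conclusion.** The concern holds in a limited form. Protocol 6.11.7 does not give one grade for a laboratory AE when local and central results differ, and the SAP does not repair this. A between-arm distortion of grade-specific tables is possible; the documents do not show that it will occur.

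The size cannot be derived. In the lipase illustration the Grade 3-4 rate ranges from 5.7% to 11.0% around 9.6%, and this rests on the assumed 10% to 50% one-grade discordance and on Phase 1 counts in a single arm. Protocol 9.8.6.1 excludes formal testing of AE incidence, and no efficacy endpoint or its type I error is touched. This is a small point, worth correcting because it takes only a few sentences.

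**What to change.** - **Protocol 6.11.7.** Delete the investigator-choice sentence. Keep one fixed rule for discordant AE grades, the same in both arms: either central-final or highest-grade. Remove the other sentence, or limit it expressly to the grading of laboratory values. Either choice ends the conflict.
- **SAP 9.2.** State that AE severity tables follow that rule.
- **SAP 9.5.** State that laboratory grades and shift tables use central results in both arms, with local results only where no central result exists for that visit.

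Use of local results for treatment decisions is unchanged.

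The cost is a few sentences. Under Protocol 11.2 a protocol change needs ethics and regulatory approval, so it could sensibly travel with another amendment. Some grade-specific rates may shift slightly.
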